4.3.1.2.2. Exclusion of implausible solicited events

Some local and systemic events will be directly measured by the participant and will be subject to a reconciliation process, even if they are biologically implausible. Therefore, these implausible measurements will be removed from the analysis but included in listings. Implausible measurements are summarized in the table below:

Table 12 Implausible Solicited Events

Parameter	Implausible measurements
Body temperature	≤ 33°C or ≥ 42°C
Erythema	Measurements < 0 mm For subjects ≥ 6 years: ≥ 900 mm
Swelling	Measurements < 0 mm For subjects ≥ 6 years: ≥ 500 mm

4.3.1.2.3. Analysis of unsolicited adverse events

The analysis of unsolicited events will be performed on Exposed Set.

4.3.1.2.4. Analysis of pregnancy outcome

The analysis of pregnancy outcome will be performed on Exposed Set.

Still births, preterm births and spontaneous abortions will be counted per pregnancy, regardless of the number of fetuses in the concerned pregnancy.

4.3.1.2.5. Analysis of RTI and LRTI

The analysis of RTI and LRTI will be performed on Exposed Set according to the case definitions in section 4.1.2.4. Separate listings of maternal RSV associated MA-RTI and infant RSV associated LRTI/hospitalization will be provided.

Further analysis with respect to the incidence of RSV LRTI by an exploratory case definition might be performed if deemed necessary.

4.3.2. Immunogenicity

4.3.2.1. Analysis of immunogenicity planned in the protocol

The secondary analysis for immunogenicity will be based on the Per Protocol – Immunogenicity Set.

	Secondary Immunogenicity Endpoints	Statistical Analysis Methods
Maternal participants	
 • Humoral immune responses at Day 31 post-dosing: 
 – RSVPreF3 IgG-specific antibody concentrations – Neutralizing antibody titers against RSV-A • Humoral immune responses at pre-dosing (Day 1), at Day 31 post-dosing and at delivery: 	
For each assay, at each timepoint and by study group and age category (<18 years; ≥ 18 years; overall):
 
 • Antibody titers/concentrations will be displayed using reverse cumulative curves. • GMTs/ GMCs will be tabulated with 95% CI and represented graphically. • GMR of antibody titers/concentrations at each post-dosing timepoint over pre-dosing will be tabulated with 95% CI. 
Between group evaluation in terms of RSVPreF3 IgG-specific antibody concentrations and neutralizing antibody

CONFIDENTIAL

	Secondary Immunogenicity Endpoints	Statistical Analysis Methods
	
 - Neutralizing antibody titers against RSV-B. 	
titers against RSV-A will be performed at Day 31 post-dosing, and against RSV-B at Day 31 post-dosing and at delivery using an ANCOVA model on the logarithm₁₀ transformation of the concentrations/titers, and including the pre-dosing logarithm₁₀ transformation of the concentrations/titers, the study intervention, gestational age at the time of study intervention administration (<28^{0/7}; ≥ 28^{0/7} weeks), and the interval between dosing and delivery as covariates if needed.

Infant participants	
 • Humoral immune responses at delivery*: 
 - Neutralizing antibody titers against RSV-B 
* Measured in cord blood sample collected at delivery or infant blood sample collected within 72 hours after birth (if no cord blood sample can be obtained).
	
For each assay, the following analysis will be performed by study group:
 
 • Antibody titers will be displayed using reverse cumulative curves. • GMTs will be tabulated with 95% CI and represented graphically. 
Between group evaluation in terms of neutralizing antibody titers against RSV-B will be performed at delivery using an ANCOVA model on the logarithm₁₀ transformation of the concentrations/titers, and including the pre-dosing logarithm₁₀ transformation of the concentrations/titers, the study intervention, gestational age at the time of study intervention administration (<28^{0/7}; ≥ 28^{0/7} weeks), and the interval between dosing and delivery as covariates if needed.
 
In addition, if cord blood samples are missing in 20% or more of infants in a single study group, and if the data permit: RSV antibody concentrations/titers in infants through time will be evaluated separately in infants with cord blood samples and in infants from whom, instead, a blood sample was obtained within 72 hours after birth.

	
 • Humoral immune responses at Day 43*, at Day 121* and at Day 181* after birth: 
 - RSVPreF3 IgG-specific antibody concentrations - Neutralizing antibody titers against RSV-A and RSV-B 
* Measured in infant blood samples collected at Day 43 (sub-cohort 1, V2-NB), at Day 121 (sub-cohort 2, V3-NB) and at Day 181 (sub-cohort 3, V4-NB) after birth. Each infant will be randomly assigned (1:1:1) to one of 3 sub-cohorts.
	
For each assay, at each timepoint and by study group:
 
 • Antibody titers/concentrations will be displayed using reverse cumulative curves. • GMTs/ GMCs will be tabulated with 95% CI and represented graphically. 
Between group evaluation in terms of RSVPreF3 IgG-specific antibody concentrations and neutralizing antibody titers against RSV-A and RSV-B at Day 43 (sub-cohort 1, V2-NB), at Day 121 (sub-cohort 2, V3-NB) and at Day 181 (sub-cohort 3, V4-NB) after birth using an ANCOVA model on the logarithm₁₀ transformation of the concentrations/titers, and including the pre-dosing logarithm₁₀ transformation of the concentrations/titers, the study intervention, gestational age at the time of study intervention administration (<28^{0/7}; ≥ 28^{0/7} weeks), and the interval between dosing and delivery as covariates if needed.

ANCOVA = Analysis of covariance; **CI** = Confidence interval; **GMR** = Geometric mean of ratio; **GMT/ C** = Geometric mean titer/ concentration; **NB** = Newborn; **RSV-A / B** = Respiratory syncytial virus subtype A / B; **RSVPreF3 IgG** = Respiratory syncytial virus PreF3 immunoglobulin G

4.3.3. Sensitivity analyses

For primary and secondary immunogenicity endpoints, between study group comparisons will also be explored through statistical modelling. This analysis is exploratory.

For the analysis of maternal participants at each time point (Day 31, Delivery), the ANCOVA model will be explored and fitted via the proc GML procedure according to the following code:

```
PROC GLM data=adis_moth;
  BY atptn atpt;
  CLASS tr01aga gagevg1 agegr3;
  MODEL aval = base tr01aga gagevg1 agegr3 vacdel;
  LSMEANS tr01aga/pdiff cl alpha=0.05;
RUN;
```

where aval represents the log-transformed antibody value of the immunogenicity variable at a given post baseline timepoint, group indicates the study group, gagevg1 is the gestational age category at study intervention administration ($<28^{0/7}$, $\geq 28^{0/7}$ weeks), agegr3 is the age category at study intervention administration (<18 years and ≥ 18 years), vacdel is the interval between vaccination and delivery (days). The inclusion of age category at study intervention administration, interaction term between age category and gestational age category and interval between study intervention administration and delivery in the model depends on the availability of the variables (vacdel may not be available at Day 31 analysis) and the necessity, therefore, the above SAS code serves as a reference and may be adjusted according to the analysis needs. Other possible co-variables which could be included in the model, but not limited to, are pre-existing HIV infection status, CD4 count, COVID-related complications.

For the analysis of infants at each time point (cord blood at Delivery, Day 43 post-birth, Day 121 post-birth, and Day 181 post-birth), similar model will be explored:

```
PROC GLM data=adis;
  BY atptn atpt;
  CLASS tr01aga gagevg1 gagebg1 agegr3;
  MODEL aval = base tr01aga gagevg1 gagebg1 agegr3;
  LSMEANS tr01aga/pdiff cl alpha=0.05;
RUN;
```

Baseline is pre-vaccination logarithm10 transformation of the concentrations/titers from maternal participants, gagebg1 is gestational age category at birth (> 37 weeks; ≤ 37 weeks) for infant participants. With the inclusion of gestational age category at vaccination (gagevg1) in the model, this categorical variable gagebg1 provides similar information as continuous variable vacdel, therefore the inclusion of either variable in the model could be adjusted according to the analysis needs. Other possible co-variables which could be included in the model, but not limited to, are maternal pre-existing HIV infection status, CD4 count, COVID-related complications, infant HIV infection status.

The ratio of GMTs/GMCs between study intervention groups and the corresponding 95% CI will then be constructed by exponentiating the mean difference and its confidence interval between study intervention groups on the logarithm10 scale estimated from the model. Summary tables will show adjusted GMT/GMC for study intervention groups, and ratios of GMTs/GMCs between study intervention groups along with the 95% CI.

Summary tables will present number of observations included in the model, the model adjusted GMT/GMC for each group and between group adjusted GMT/GMC ratio with the corresponding 95% CIs at each timepoint.

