4.3. Justification for dose (Amended 15 March 2022)

A single formulation of the investigational RSV maternal vaccine (containing 120 µg of the RSVPreF3 antigen) *was* planned. Available data *suggested* that the 120 µg formulation *had* an acceptable safety profile and tends to elicit stronger immune responses, which is likely to result in higher placental transfer of antibodies to the fetus than formulations containing 30 or 60 µg of the RSVPreF3 antigen. Available results from RSV MAT-001 and RSV MAT-004 studies are included in the IB to support RSV MAT-012.

Infection with RSV occurs in almost all participants by the time of reproductive age and it is extremely unlikely that a maternal participant would not have been naturally infected with RSV before. Results of study RSV MAT-001 in non-pregnant women *and RSV MAT-004 in pregnant women* indicate that a single dose of the study vaccine is sufficient to boost the neutralizing antibodies induced by previous natural infections.

The study vaccine will be administered* between 24^{0/7} and 36^{0/7} weeks of gestation (inclusive). This gestational age range is considered optimal for both immunogenicity and safety. It allows enough time to (a) induce high neutralizing antibody levels in maternal participants before term delivery and (b) ensure these antibody levels are elevated during the period of greatest placental antibody transfer to the fetus. Moreover, it is after the critical period for organogenesis (i.e. after the period when most congenital abnormalities develop).

**** Due to the recent safety signal, there will be no further enrollment and vaccination of maternal participants. For details, refer to [Section 2.3](#).***

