5. SAMPLE SIZE DETERMINATION

Approximately 378 maternal participants* will be randomized in a 2:1 ratio to achieve at least 340 evaluable maternal participants (including at least 16 evaluable adolescents from 15 to less than 18 YOA).

Participants who withdraw from the study will not be replaced.

**** Due to the recent safety signal in RSV-MAT-009, there will be no further enrollment and vaccination of maternal participants.***

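### If residual spread differs between arms, the single pooled variance in the 2:1 antibody ANCOVA would mis-size the adjusted GMT/GMC and ratio intervals; an arm-specific or robust variance avoids this

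*SAP*

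**What the plan says.** SAP 4.3.3 gives the maternal code: "PROC GLM data=adis_moth", then "MODEL aval = base tr01aga gagevg1 agegr3 vacdel", then "LSMEANS tr01aga/pdiff cl alpha=0.05". The terms are baseline log titre, treatment, gestational-age category at dosing, age category and the dosing-to-delivery interval. There is no arm-specific variance, robust standard error or residual check. A similar model is given for infants.

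The output is described in the same section: "Summary tables will present number of observations included in the model, the model adjusted GMT/GMC for each group and between group adjusted GMT/GMC ratio", with 95% CIs.

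SAP 5 says that mothers "will be randomized in a 2:1 ratio to achieve at least 340 evaluable maternal participants". SAP 5.2 takes 226 evaluable vaccinees, a 10% non-evaluable rate, and log10 SDs of 0.3 and 0.4 from earlier PreF2 studies. No SD is given for placebo.

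Sections 4.2.2.1 and 4.3.2.1 list this ANCOVA as the between-group evaluation for the primary and secondary immunogenicity endpoints. Section 4.3.3 calls the modelling exploratory, and section 2 says that no hypothesis is tested.

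**The concern.** PROC GLM as written estimates one residual variance and applies it to both arms. With twice as many vaccinees, that estimate is dominated by the vaccine arm. If the arms differ in residual spread, the ratio CI and both per-arm adjusted CIs inherit the wrong variance.

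There is a reason to expect a difference. Protocol 4.3 says that "a single dose of the study vaccine is sufficient to boost the neutralizing antibodies" from earlier infection, and only one arm receives that dose. Once baseline is in the model, an unboosted woman's delivery titre may track her own starting value closely, while a vaccinee's also carries her individual response to the dose. In a descriptive trial the intervals are the inferential output, so their calibration is what is at stake.

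**Working it through.** **1. The plan's own precision figure.** SAP Table 14 gives half-widths of 0.056 (SD 0.3) and 0.074 (SD 0.4) for the log10 fold increase, n = 226.

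- Formula: t(0.975, 225) × SD × √2 / √226, with t = 1.971.
- SD 0.3: 1.971 × 0.3 × 1.414 / 15.03 = 0.0556. SD 0.4: 0.0742. Both match.
- Without √2 the results are 0.039 and 0.052, which do not match.

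So 0.3 and 0.4 act as titre SDs, with pre- and post-dose values treated as uncorrelated. They are not residual SDs by arm.

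**2. Inputs for the variance check.** Vaccine n1 = 226 (SAP 5.2). Placebo n0 = 126 × 0.9 ≈ 113 (planned 126, same 10% rule). The residual SDs s1 (vaccine) and s0 (placebo) are assumptions. For scale, a residual SD of 0.3 or 0.2 from a titre SD of 0.4 implies a pre/post correlation of √(1 − 0.75²) = 0.66 or √(1 − 0.5²) = 0.87.

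**3. Formulas.**

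- Pooled variance: sp² = (225 s1² + 112 s0²) / 337
- SE used for the log ratio: √[sp² (1/226 + 1/113)]
- Correct SE: √(s1²/226 + s0²/113)
- Coverage: 2Φ(t × SE used / correct SE) − 1, with t(0.975, 337) = 1.967
- For a single arm, the SE ratio is sp/s1 or sp/s0

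Worked case, 0.4/0.3: sp² = (36 + 10.08)/337 = 0.1367, so sp = 0.370. SE used = 0.0426 and correct SE = 0.0388, a factor of 1.10. Per arm: 0.370/0.4 = 0.924 and 0.370/0.3 = 1.233.

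| SD vaccine/placebo | SE used | Correct SE | Factor | Ratio-CI coverage | Vaccine GMT coverage | Placebo GMT coverage |
|---|---|---|---|---|---|---|
| 0.4/0.4 | 0.0461 | 0.0461 | 1.00 | 95% | 95% | 95% |
| 0.4/0.3 | 0.0426 | 0.0388 | 1.10 | 96.9% | 93.1% | 98.5% |
| 0.4/0.2 | 0.0399 | 0.0326 | 1.23 | 98.4% | 91.2% | 99.9% |
| 0.3/0.4 | 0.0388 | 0.0426 | 0.91 | 92.7% | 97.3% | 90.2% |

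On the ratio scale, the CI is the estimate ×/÷ 1.213 where 1.192 is correct (0.4/0.3), 1.198 for 1.159 (0.4/0.2), and 1.192 for 1.213 (0.3/0.4).

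**4. Role of the allocation.** At 113:113 the ratio factor is 1.00 for every SD pair tried. The unequal allocation creates the ratio-CI error. The per-arm error remains at 1:1.

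**5. Simulation.** An ANCOVA with covariates, 8,000 runs per case, gave pooled-variance coverage of the ratio CI of 96.8% (0.4/0.3), 98.4% (0.4/0.2), 92.3% (0.3/0.4) and 95.0% (0.35/0.35). HC3 standard errors gave 95.1% to 95.3% in all four. HC3 was simulated for the ratio only, not for the per-arm means.

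**6. A milder scenario.** A separate simulation kept the titre SD at 0.4 in both arms and fitted the common baseline slope, with pre/post correlation 0 in vaccinees and 0.66 to 0.87 in placebo. The ratio SE was 4% to 12% too large, with coverage of 95.8% to 97.2%. The shared slope leaves more residual spread in placebo than an arm-specific slope would, so the larger factors in the table lean towards the extreme.

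**The case against.** The strongest reply is that nothing has been shown to be wrong, and that stands. A reader might infer that the planned intervals are mis-sized, or that the ratio CI is necessarily too wide. The documents support neither. They contain no placebo SD and no residual SD by arm. The statement about boosting concerns level, not spread. Equal SDs give no error, and a smaller vaccine-arm SD reverses every direction. The sizes above also rest on the planned 226 and 113, and enrolment stopped early.

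The consequence is limited as well. The modelling is exploratory, with no margin or decision rule. A shift between ×/÷ 1.19 and ×/÷ 1.21 is small beside an anticipated 9- to 12-fold rise. SAP 4.1.1 bases the unadjusted GMT/GMC CIs on Student intervals for the mean log value, and these are tabulated by study group, so arm-level precision without cross-arm pooling is reported anyway. Section 4.1.1 also has a general rule for ratio CIs that is not tied to PROC GLM.

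Section 4.3.3 says that the code is a reference and may be adapted. That helps less: the changes it names are covariates and an interaction, not the variance.

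A reader might also object to the SAP's remark that "this categorical variable gagebg1 provides similar information as continuous variable vacdel", or to the two-category gestational age at dosing. Neither carries this point. The remark concerns the infant model, where the per-protocol set excludes births under 4 weeks after dosing and either variable may be used. The maternal model already contains the continuous interval, and the 28-week split is a minimization factor.

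**Conclusion.** The point holds conditionally. The specified code imposes a common residual variance at 2:1 allocation and includes no safeguard, and it supplies the only between-group comparison listed in the immunogenicity endpoint tables. If residual spread differs by arm, the adjusted intervals would be mis-sized: by about 10% in the SE of the log ratio when the SDs are 0.3 and 0.4 in either order, and by more with a wider gap. That rests on assumed SDs, planned numbers and, for infants, no calculation at all. It is an inexpensive improvement to an exploratory analysis. It does not invalidate any planned result.

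**What to change.** In the maternal model of SAP 4.3.3, pre-specify one of the following for the LS means and their difference:

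- arm-specific residual variances, using PROC MIXED with `REPEATED / GROUP=tr01aga` and Kenward-Roger or Satterthwaite degrees of freedom; or
- heteroscedasticity-consistent (HC3) standard errors.

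Do the same in the infant model where sample numbers permit. Collection at Days 43, 121 and 181 has stopped, so arm-specific variances may be poorly estimated there. A baseline-by-arm term is not needed for this fix.

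Because the study is already unblinded, the choice should be written down before the model is run on titres by arm. The cost is a code change and, for the first option, one extra variance parameter per model. No new data are needed. In the equal-SD simulation, HC3 coverage of the ratio CI was 95.3%, so no loss was visible.

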9.4.6. Other analyses

9.4.6.1. Demography and baseline characteristics analyses

These analyses will be performed on the ES and on the FAS for immunogenicity.

For all maternal participants, demographic characteristics (e.g., age at study intervention administration (<18 years; ≥ 18 years; overall), gestational age at study intervention administration (<28^{0/7}; ≥ 28 ^{0/7} weeks), geographic ancestry) will be summarized by group using descriptive statistics. The interval in days between maternal study intervention and delivery will be calculated and summarized by group using descriptive statistics.

For their infants, demographic characteristics (e.g., gestational age at time of delivery (> 37 weeks; ≤ 37 weeks), sex, weight, length, head circumference, geographic ancestry, APGAR score), and lifestyle characteristics (e.g., living environment, household composition, breastfeeding, passive smoking and extent of contact with children less than 6 YOA) will be summarized by group, and for each immunogenicity sub-cohort within each group, using descriptive statistics.

- Frequency tables will be generated for categorical variable such as geographic ancestry.
- Mean, median, SD and range will be provided for continuous data such as age.

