3	(MAY apply to LMIC- or may be non-viable in LMIC) Live-born infant AND Gestational age ≥7 months but <9 months according to parent/family member/delivery attendant (GA Level of Certainty = 2 OR 3) AND Death of infant in first 28 days of life AND Medically-confirmed death OR non-medically-confirmed death
Neonatal death in a term live birth	
Level	Description
1	Live-born infant AND Gestational age ≥37 weeks (GA Level of Certainty = 1) AND 
 • Birth weight >2500 g OR • Documented intrauterine growth retardation if ≤2500 g AND Death of infant in first 28 days of life AND Medically-confirmed death

Neonatal death in a term live birth (continued)	
Level	Description
2	Live-born infant AND Gestational age/size of newborn assessed as one or more of: 
 • Gestational age ≥ 37 weeks (GA Level of Certainty = 1 OR 2) • Birth weight ≥ 2500 g AND Death of infant in first 28 days of life AND Medically-confirmed death OR non-medically-confirmed death which is confirmed by examination by (by at least) non-medically-trained attendant (e.g. undertaker, community member)
3	(apply to Lower Middle Income Countries) Live-born infant AND 2. Gestational age ≥ 9 months according to parent/family member/delivery attendant (GA Level of Certainty = 2 OR 3) AND 
 • Death of infant in first 28 days of life AND 
 • Medically-confirmed death OR non-medically-confirmed death

Reference: Pathirana J, Munoz FM, Abbing-Karahagopian V, et al. Neonatal death: Case definition & guidelines for data collection, analysis, and presentation of immunization safety data. *Vaccine*. 2016;34(49):6027-6037.

Table 39 Preterm Birth

Birth in less than 37 gestation-completed weeks (less than 259 days).

Prematurity and assessment of gestational age	
Level	Description
1	Certain last menstrual period date (LMP) LMP or intrauterine insemination (IUI) date or embryo-transfer (ET) date with confirmatory 1st trimester scan ($\leq 13^{6/7}$ weeks). OR 1st trimester scan ($\leq 13^{6/7}$ weeks)
2a	Certain LMP* with 2nd trimester scan ($14^{0/7}$ weeks to $27^{6/7}$ weeks). Note: If LMP and U/S do not correlate, default to U/S GA assessment. OR Certain LMP* with 1st trimester physical examination.
2b	Uncertain LMP with 2nd trimester scan ($14^{0/7}$ weeks to $27^{6/7}$ weeks).
3a	Certain LMP with 3rd trimester scan $\geq 28^{0/7}$ weeks.

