4.2. Primary Endpoint(s) Analyses

4.2.1. Safety

4.2.1.1. Analysis of safety and reactivity planned in the protocol

Safety analyses in maternal participants will include summaries by study group and age category (<18 years; ≥ 18 years; overall) of solicited administration site and systemic events, unsolicited AEs, MAEs, SAEs, MA-RTIs, RSV-associated MA-RTIs, (S)AEs leading to study withdrawal, worsening of pre-existing medical conditions and/or obstetric complications, pregnancy outcomes and pregnancy-related AESIs.

Safety analyses in infant participants will include summaries by study group and gestational age at birth (≥ 37 weeks; <37 weeks; overall) of neonatal AESIs, MAEs, SAEs, (S)AEs leading to study withdrawal, and occurrence of RSV- associated LRTIs, severe LRTIs, RSV-associated hospitalization.

The reactivity analysis will be performed on Solicited Safety Set for maternal participants, and other safety analyses will be performed on the Exposed Sets for both maternal and infant participants.

	Primary Safety Endpoints	Statistical Analysis Methods
Maternal participants	Number and percentage of maternal participants reporting solicited administration site and systemic events during a 7-day (i.e. Day 1 to Day 7 included) follow-up period after dosing.	
The number and percentage with exact 95% CI of maternal participants reporting each solicited administration site event (any grade, each grade,) and solicited systemic event (any, each grade) during the 7-day (7 days post-study intervention, Day 1 included) follow-up period after dosing will be tabulated by maximum intensity per participant for each study group.
 
The number and percentage of maternal participants reporting:
 
 • at least one administration site AE (solicited and unsolicited) • at least one systemic AE (solicited and unsolicited) • any AE 
during the 7-day (7 days post-study intervention, Day 1 included) follow-up period after dosing will be tabulated with exact 95% CI by group.
 
The same computations will be done for Grade 3 solicited and unsolicited AEs, for any unsolicited AEs considered related to study intervention, for any Grade 3 unsolicited AEs considered related to study intervention and for any solicited and unsolicited AEs resulting in a medically attended visit (i.e., MAEs).

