4.6.2. Subgroup analyses

Subgroup analyses of the primary endpoints will be made to assess consistency of the intervention effect across the following subgroups:

- Age group (for maternal participants): < 18 vs ≥ 18 years
- Gestational age at birth (for infant participants): ≥ 37 weeks; < 37 weeks (as assessed by the GAIA gestational age definition*)
 - * Additional statistical analyses may also be performed by using the Intergrowth-21st (IG-21) standard definition [Villar, 2014].
- Pre-existing HIV infection status: present vs absent (for maternal participants ≥ 18 YOA only)
- Pre-existing obstetric complications: present vs absent (for maternal participants ≥ 18 YOA only)

Except for maternal age group, if the number of participants is too small (less than 10%) within above mentioned subgroup, then the subgroup categories may be redefined prior to final analysis.

To take a more practical approach, subgroup analysis of safety by age category at study intervention administration (< 18 ; ≥ 18 years) in maternal participants will include summaries of solicited administration site and systemic events, unsolicited AEs, MAEs, SAEs, RSV-associated MA-RTIs, (S)AEs leading to study withdrawal, worsening of pre-existing medical conditions and/or obstetric complications, pregnancy outcomes and pregnancy-related AESIs.

Subgroup analysis of safety by gestational age at birth (≥ 37 weeks; < 37 weeks) in infant participants will include summaries of neonatal AESIs, MAEs, SAEs, (S)AEs leading to study withdrawal, and occurrence of RSV-associated LRTIs, any severity and severe LRTIs, RSV-associated hospitalization.

Subgroup analysis on other safety summaries will be performed if deemed necessary.

Subgroup analysis of immunogenicity by age category at study intervention administration (< 18 ; ≥ 18 years) for maternal participants and by gestational age at birth (≥ 37 weeks; < 37 weeks) for infant participants will include analysis of GMT(C) and GMR calculation at each time point and geometric mean of placental transfer.

Subgroup analysis on other immunogenicity analysis will be performed if deemed necessary.

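### Exploratory ANCOVA in SAP 4.3.3: default LSMEANS gives adolescents half the weight in adjusted GMTs if age category is kept, and `gagebg1` is cut at >37/≤37 instead of ≥37/<37 weeks

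*SAP*

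**What the plan says.** SAP 4.3.3 supplements the immunogenicity endpoints with exploratory PROC GLM models. The maternal model lists treatment, gestational age at dosing (`gagevg1`, <28 or ≥28 weeks) and age category (`agegr3`, <18 or ≥18 years) as CLASS effects, with baseline and the dosing-to-delivery interval (`vacdel`) as continuous covariates. The infant model replaces `vacdel` with gestational age at birth (`gagebg1`). Each model ends with "LSMEANS tr01aga/pdiff cl alpha=0.05". The summary tables are to show "the model adjusted GMT/GMC for each group and between group adjusted GMT/GMC ratio with the corresponding 95% CIs at each timepoint".

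The planned adolescent share is small. SAP section 5 aims for 340 evaluable women, "including at least 16 evaluable adolescents from 15 to less than 18 YOA".

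On the birth cut, SAP 4.3.3 states that "gagebg1 is gestational age category at birth (> 37 weeks; ≤ 37 weeks) for infant participants". Protocol 9.4.6.1 has the same wording for infant demography: "gestational age at time of delivery (> 37 weeks; ≤ 37 weeks". The infant safety summaries in SAP 4.2.1.1 use "gestational age at birth (≥ 37 weeks; <37 weeks; overall", and the subgroup list in SAP 4.6.2 uses "Gestational age at birth (for infant participants): ≥ 37 weeks; < 37 weeks". SAP 4.3.1.1, 6.1.2.1 and 6.1.2.2 follow the second form. Protocol Appendix 9 (Table 39) defines preterm birth as "Birth in less than 37 gestation-completed weeks (less than 259 days".

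**The concern.** Without OM, LSMEANS in PROC GLM gives each level of the other CLASS factors equal weight. This is software behaviour, not SAP text, and the SAP names no reference population. With a two-level age factor, each adjusted GMT or GMC would describe a population that is half adolescent. A reader of the table would see a group mean with a wider interval than the raw one, possibly shifted, and no explanation.

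The cut is a separate consistency matter. Under ≤37, births at 37+0 fall in the same category as preterm births. If only completed weeks are stored, all of week 37 does. The rest of the SAP counts those infants as term.

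**Working it through.** **Planned figures.** 18/378 = 4.8%, which the protocol synopsis rounds to 5%. 378 × 0.9 = 340.2 and 252 × 0.9 = 226.8 agree with the stated 340 and 226 evaluable. Placebo is then 340 − 226 = 114. The 16 adolescents split about 11:5 under 2:1 allocation.

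**Weight.** The default is 0.50 and the observed margin is 16/340 = 0.047, so the default is 0.50/0.047 = 10.6 times the planned share.

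**Between-group ratio.** No model has a treatment-by-age term, so the weights cancel in the difference between groups. Its SE, for an assumed residual SD of 0.4, is 0.4 × √(1/226 + 1/114) = 0.046 under either weighting.

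**SE of each adjusted log10 mean.** In an additive model with roughly uncorrelated factors,

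SE² ≈ SD² × [1/n_group + Σ (0.5 − p)² × (1/n₁ + 1/n₂)],

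summed over the other two-level factors, where p is the observed share and n₁, n₂ are the level counts. With OM the sum is zero. The ratio of the two SEs does not depend on the SD.

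- Group terms: 1/226 = 0.004425; 1/114 = 0.008772.
- Age: (0.453)² × (1/16 + 1/324) = 0.01346.
- Gestational age at dosing (share dosed before 28 weeks assumed, since the documents give none): at 50% the term is 0; at 20% it is 0.09 × (1/68 + 1/272) = 0.00165; at 10% it is 0.16 × (1/34 + 1/306) = 0.00523.

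Resulting SE ratios, default to OM:

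- 50% early: vaccine √(0.01788/0.004425) = 2.01; placebo √(0.02223/0.008772) = 1.59.
- 20% early: vaccine √(0.01953/0.004425) = 2.10; placebo √(0.02388/0.008772) = 1.65.
- 10% early: vaccine √(0.02311/0.004425) = 2.29; placebo √(0.02746/0.008772) = 1.77.

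Repeating this with full design matrices gives the same values to within 0.01. Adding `vacdel`, which is correlated with gestational age at dosing, raises them to about 2.14-2.18 and 1.68-1.71 at 20% early (depending on the assumed dosing-to-delivery distribution) and to about 2.4 and 1.85 at 10%.

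**Infant model.** Assume one infant per mother and 15% of births at or below the cut. The extra term is (0.35)² × (1/51 + 1/289) = 0.00283. At 50% and 20% early the ratios become 2.16 and 2.25 (vaccine) and 1.69 and 1.74 (placebo), so the picture is similar.

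**Illustration on the titre scale.** With an assumed residual SD of 0.4 and 20% early, the vaccine SE is 0.4 × √0.01953 = 0.056, against 0.4 × √0.004425 = 0.027. The 95% CI is then a factor of about 1.29 either side of the adjusted GMT, against 1.13. SAP 5.2 gives 0.3-0.4 as titre SDs from studies of another vaccine, not as residual SDs.

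**Possible shift.** Each adjusted GMT moves by 10^(0.453 × d), where d is the adolescent-minus-adult log10 difference. An assumed d of ±0.1 gives 1.11 or 0.90. The documents report no such difference.

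**Sensitivity to counts (maternal delivery model, 20-50% early).** At 25%, 50% or 75% of planned size with about the same adolescent share, the ratios stay at 2.00-2.15 (vaccine) and 1.58-1.69 (placebo). At full size, an adolescent share of 2.4% gives about 2.8-2.9 for vaccine, and 10% gives 1.5-1.6.

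**Without `agegr3`.** The inflation is smaller but has no fixed ceiling. With `vacdel` in the model, two assumed dosing-to-delivery distributions gave 1.23 and about 1.29 for vaccine (1.12 and 1.16 for placebo) at 20% early. At 10% early the figures were about 1.63 and 1.35.

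**The case against.** The best defence is that little depends on this. SAP section 2 tests no hypotheses, and SAP 4.3.3 is exploratory and aims at the between-group comparison, which the weighting does not touch. The SAP makes age category optional and calls the code adjustable. The ANCOVA described for the endpoints in SAP 4.2.2.1 and 4.3.2.1 has no age term. Equal-weight LS-means are a recognised convention. Maternal GMTs are tabulated by age category and overall, and infant GMTs by study group, so a discrepancy with the adjusted column would be visible. `gagebg1` is optional too, because SAP 4.3.3 allows a choice between it and `vacdel`.

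All of that stands, and it limits importance. It does not say what population a tabulated adjusted GMT describes, and it does not reconcile two definitions of the same category.

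A reader might infer more than the documents support:

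- That the vaccine-placebo comparison or the unadjusted GMTs are affected by the weighting. They are not.
- That the adjusted GMTs will be off by some stated percentage. No adolescent-adult difference is given.
- That infant results by maternal age are nowhere foreseen. SAP 4.6.1 promises sub-analyses of objectives and endpoints in the 15-17 subgroup. Its heading refers to maternal participants, so its reach to infants is arguable, but a flat denial would go too far.
- That the cut alters the preterm-birth endpoint. It defines a model covariate, and a demography category in the protocol.

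**Conclusion.** Both parts hold, and both are minor. If `agegr3` stays in the model, the adjusted GMT/GMC column gives adolescents 50% of the weight against a planned minimum share of 4.7%. At planned counts with 20-50% dosed early, its SE is about 2.0-2.2 times (vaccine) and 1.6-1.7 times (placebo) the observed-margin SE, and about 2.4 and 1.85 times at 10% early. The infant model behaves similarly. These figures rest on the planned counts and an assumed early-dosed share. Enrolment stopped, so the real numbers may differ. If no adolescent is in the analysed set, the age issue does not arise.

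The `gagebg1` cut contradicts five other places in the SAP and the protocol's own preterm definition. Its effect on results cannot be quantified from the documents, so it is a consistency correction.

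**What to change.** Add OM to both LSMEANS statements. State in SAP 4.3.3 that adjusted GMTs/GMCs use the observed margins of the participants analysed, that is, those with a result at both baseline and the timepoint concerned (SAP 4.1.1). Redefine `gagebg1` as ≥37/<37 weeks in SAP 4.3.3 and align Protocol 9.4.6.1 with it. The cost is one option in two code statements, one derivation line and a few words of text. No new data are needed, and the OM change leaves the between-group ratio as it is.
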